**Visit 8 (4 to 21 days after visit 6), 9 (11 to 13 weeks after visit 2), 10 (23 to 25 weeks after visit 2)**

- I. SCID for visits 9 and 10 only
- II. Vital Signs for visit 8 only
- III. Bloods (see Appendix B and section 7.9.2 for details of the tests that will be used),
- IV. Urine Drug Screen (See Appendix B and section 7.9.2 for details of the tests that will be used.)
- V. Breathalyser
- VI. SCRAM-X removal (visit 8 only)
- VII. Relapse Prevention Based Cognitive Behavioural Therapy for visit 8 only
- VIII. Adverse Events Review
- IX. Concomitant medication review
- X. Alcohol and Drug use History
- XI. BDI
- XII. HAM-D
- XIII. POMS
- XIV. STAI
- XV. ACQ-NOW
- XVI. BPRS
- XVII. PSI

- XVIII. Alcohol Timeline Follow Back
- XIX. Drink diary
- XX. Fagerstrom Nicotine Dependence
- XXI. Craving VAS
- XXII. SF-12
- XXIII. Prose Recall
- XXIV. Delay Discounting (monetary choice questionnaire)
- XXV. Stop Signal Reaction time
- XXVI. Working Memory (digit span WAIS-IV)
- XXVII. Adverse Effects VAS
- XXVIII. Pattern Recognition Test

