- The Alcohol TimeLine Follow Back (TLFB) is a drinking assessment method that obtains estimates of daily drinking and has been evaluated with clinical and nonclinical populations. Using a calendar, people provide retrospective estimates of their daily drinking over a specified time period. Several memory aids can be used to enhance recall (e.g., calendar; key dates serve as anchors for reporting drinking; standard drink conversion). The Alcohol TLFB has been shown to have good psychometric characteristics with a variety of drinker groups, and can generate variables that provide a wide range of information about an individual's drinking (e.g., pattern, variability, and magnitude of drinking).
- A drink diary will be given to each participant to take home in between Visits 8, 9 and 10. Participants will be asked to record their alcohol consumption every day in between study visits. Drink diaries are regularly used in alcohol research to record subjective alcohol consumption.
- Alcohol Craving Questionnaire - short-form (ACQ-NOW) is a 12-item scale that assesses current alcohol craving.

Validated Neurocognitive measures:

- Delay discounting (e.g. monetary choice questionnaire): this is a task that measures an individual's preference for immediate small award over a long term bigger gain.
- Prose recall task: this looks at episodic memory by testing participants recall of a short news broadcast.

- Stop signal task: Stop signal reaction time examines response inhibition, participants have to inhibit prepotent responses to stimuli on the screen when they see a cue or 'stop signal'.
- Working memory task (e.g. digit span WAIS-IV): Working memory measures an individual's ability to maintain and manipulate small amounts of information.
- Pattern recognition memory task (BPS-O Task) is a memory task that taps hippocampal functioning and requires participants to distinguish between perceptually similar items that they have seen before and those they have not.

Questionnaires that are not validated:

- The Pre-Screening questionnaire has been developed to assess suitability for inclusion into the trial.
- Adverse Effects Visual Analogue Scale (VAS) has been developed to measure adverse events during the ketamine infusion and treatment.
- Craving VAS: a one item visual analogue scale will be used to assess craving for alcohol anchored at one end with 'No desire to drink alcohol' and the other 'Very strong desire to drink alcohol'.

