## **7.10 Definition of end of trial**

The end of the trial will be the last follow-up visit of the participant at 23 to 25 weeks post visit 2.

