### **13.1 Outcomes**

#### ***13.1.1 Primary outcomes***

Relapse rates at 6 months

Percentage Days Abstinent at 6 months

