### **13.3.2 Primary outcome analysis**

There are two primary outcomes: (i) proportion relapsed (recommenced using alcohol) at 6-month follow-up; and (ii) percentage of days abstinent at 6-month follow-up (the denominator being 175 days). The proportion of relapsed participants at 6-month follow-up will be reported as a percentage for each arm, as well as for the ketamine arms combined and

the psychotherapy arms combined. Although no formal power calculations for a between-group analysis have been performed, the proportion of relapsed participants at 6-month follow-up will be expressed as a relative risk (RR) with a 95% confidence interval for the following comparisons: (i) all ketamine participants versus all non-ketamine participants; (ii) ketamine + psychotherapy participants versus ketamine + non-psychotherapy participants; and (iii) ketamine + psychotherapy participants vs. placebo + no psychotherapy participants. These analyses are purely exploratory and should be viewed with caution both in the light of lack of power and multiple testing. Percentage of days abstinent at 6-month follow-up will be reported descriptively in the same way by arm and combination of arms; additionally, the between-group mean differences and 95% confidence intervals will be reported for the comparisons set out above; again, these analyses should be regarded as exploratory. The primary analysis will be an intention-to-treat (ITT) complete case analysis including all randomised participants. A secondary analysis will be conducted including only those participants deemed to have completed to a sufficient degree their allocated interventions, that is, a per protocol analysis. All analyses will be performed by a statistician who is blinded to the treatment allocations and will be performed using Stata v.13.

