4.4 Study design

KARE has two interventions (drug therapy and psychological therapy), each with two possible forms, resulting in a two by two factorial intervention design, with a total of four possible interventions (Section 4.1).

The drug intervention will be administered by the site anaesthetist, who will be blinded to drug allocation and psychotherapy allocation. Psychotherapy/psychoeducation will be administered by the trial psychologists at each site who will be blinded to the drug allocation. Participants will also be blinded to drug allocation. Participant outcome data will be collected by site investigators who are blinded to drug allocation. The trial statistician will be blinded to both drug allocation and psychotherapy allocation throughout the trial.

Participants will be randomised to the trial after eligibility has been confirmed via prescreening and screening, and after having provided informed consent. The SCRAM-X ankle monitor (measuring alcohol levels in sweat) will be attached at screening. Treatment will commence as soon as possible after randomisation, and continue for a period of 3 weeks (one infusion session and two sessions of psychological therapy/psychoeducation per week). Follow-up data will be collected at 3 and 6 months after baseline. The last follow-up visit is scheduled for 24 weeks post baseline.

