5.2 Endpoints

The primary and secondary outcome variables are set out in the Protocol, Final Version 12, 20.01.2020, Section 13.1 (reproduced in Table 2). There are two primary outcomes:

- 1) relapse (defined as 5 drinks (8.1 units alcohol) in men and 4 drinks (6.5 units alcohol) in women on a single occasion) at 6-month follow-up; binary outcome; and
- 2) percentage days abstinent (not using alcohol at all) at 6-month follow-up; percentage, to be analysed as a continuous variable.

The two primary outcomes are to be derived from timeline follow-back.

There are 19 secondary variables, derived from 16 secondary outcomes (Protocol, Final Version 12, 20.01.2020, Section 13.1.2; depression is measured by two variables, Beck Depression Inventory and Hamilton Depression Scale; Short Form Health Survey 12 (SF-12) produces a physical and a mental component scale; psychotic symptoms is measured by two variables, Brief Psychiatric Rating Scale and Psychotomimetic States Inventory).

- 1) maximum number of days of continuous abstinence within the first 3 months (time-line follow back); continuous;
- 2) percentage days abstinent at 3 months (time-line follow back); percentage, to be analysed as a continuous outcome;
- 3) Profile of Mood states; continuous;
- 4) Beck Depression Inventory; continuous;
- 5) Hamilton Depression Scale; continuous;
- 6) Speilberger Trait Anxiety Inventory; continuous;
- 7) Brief Psychiatric Rating Scale; continuous;
- 8) Psychotomimetic States Inventory; continuous;
- 9) Fagerstrom Test of Nicotine Dependence (FTND; smokers only); continuous;
- 10) Alcohol craving (visual analogue scale); continuous;
- 11) Alcohol Craving Questionnaire - short-form (ACQ-NOW);
- 12) Short Form Health Survey 12 (SF-12), physical component scale (PCS); continuous;
- 13) Short Form Health Survey 12 (SF-12), mental component scale (MCS); continuous;
- 14) episodic memory (Prose Recall); continuous;
- 15) delay discounting; continuous;
- 16) response inhibition (Stop Signal Reaction time); continuous;
- 17) working memory; continuous;
- 18) hippocampal functioning (Pattern Recognition Test); continuous; and
- 19) adverse effects (visual analogue scale); continuous.

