5.3 Derived variables

The only derived variables will be the binary relapse variable and the number/percentage of days abstinent, to be derived from timeline follow-back data. Further details are to be confirmed.

6 General analysis considerations

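### Percentage days abstinent, a primary outcome, is divided by a fixed 175 days although visit 10 may fall on any day from 161 to 175, so full abstinence scores between 92% and 100% by visit date alone

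*Protocol*

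**What the plan says.** Protocol 13.1.1 lists "Percentage Days Abstinent at 6 months" as a primary outcome, and Protocol 13.3.2 fixes how it is scaled: "percentage of days abstinent at 6-month follow-up (the denominator being 175 days".

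Protocol 7.7 sets the timing of the last visit as visit "10 (23 to 25 weeks after visit 2", and Protocol 7.10 defines the end of the trial as "the last follow-up visit of the participant at 23 to 25 weeks post visit 2". The protocol summary gives 24 weeks per participant, and SAP 4.4 agrees: "The last follow-up visit is scheduled for 24 weeks post baseline".

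On the data source, SAP 5.2 states: "The two primary outcomes are to be derived from timeline follow-back". Protocol 7.9.1 describes that instrument as one in which "people provide retrospective estimates of their daily drinking over a specified time period". SAP 5.2 does define an abstinent day (no alcohol at all), but neither document says on which day counting starts and stops. SAP 5.3, where the derivation belongs, says only "Further details are to be confirmed". It neither repeats nor replaces the 175.

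**The concern.** The denominator assumes that everyone is observed for the longest follow-up the visit window allows. A participant seen earlier has fewer days on which abstinence could have been recorded but is still divided by 175. The days between the visit and day 175 cannot be recovered: the instrument is retrospective and visit 10 is the last contact. In effect they count as drinking days. This sits badly with Protocol 13.3.4, which declines to assume that a participant lost to follow-up had or had not relapsed.

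Two participants with the same drinking pattern therefore receive different scores because of an appointment date. Arm means are understated even if timing is balanced. SAP 6.4 reports no p-values, so the point estimates and 95% confidence intervals are what the trial delivers on this outcome, and their scale matters.

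There is also a route by which visit date could depend on drinking. Under Protocol 7.9.1, a randomised participant with a non-zero breathalyser reading has the visit ended and is invited back within the window. A participant drinking around visit 10 could thus be seen later and gain covered days. The documents do not allow the size of this effect to be estimated.

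**Working it through.** **Inputs**
- Denominator: 175 days (Protocol 13.3.2).
- Visit 10 window: 23 to 25 weeks after visit 2 (Protocol 7.7, 7.10, Appendix B).
- Scheduled date: 24 weeks (SAP 4.4; protocol summary).
- Assumption: the numerator is the number of alcohol-free days from visit 2 to visit 10.

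**Where 175 comes from.** 25 x 7 = 175, exactly the upper limit of the window. The other two dates are 23 x 7 = 161 and 24 x 7 = 168. The largest number of unobserved days for a visit within the window is 175 - 161 = 14.

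**Score by visit date.** With p the proportion of observed days that were abstinent and d the number of days from visit 2 to visit 10, the score is 100 x p x d / 175.

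| Visit 10 | d | d / 175 | p = 100% | p = 75% |
|---|---|---|---|---|
| Week 23 | 161 | 0.920 | 92.0% | 69.0% |
| Week 24 | 168 | 0.960 | 96.0% | 72.0% |
| Week 25 | 175 | 1.000 | 100.0% | 75.0% |

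Counting one day more or less does not change the picture. At full abstinence the three scores become 91.4% to 92.6%, 95.4% to 96.6% and 99.4% to 100.6%.

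**Effect on the comparison**
- If visits centre on week 24 and timing is alike in the arms and unrelated to abstinence, means and true differences are multiplied by 0.960. A true 10-point difference reads 10 x 0.960 = 9.6.
- If visit dates were spread evenly over days 161 to 175 (an assumption), date alone would give fully abstinent participants a standard deviation of about 2.5 points.
- If mean timing differed between arms, each day would add 100 / 175 = 0.57 points at full abstinence. A seven-day difference would add 7 x 100 / 175 = 4.0 points. Nothing in the documents suggests a value for this difference.

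**Check of the remedy.** Dividing by the participant's own days gives 161/161 = 168/168 = 175/175 = 100% for full abstinence at every visit date.

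**The case against.** Four objections deserve an answer.

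1. **The scores rest on an assumed counting period.** This is true. Timeline follow-back is also taken at screening and visit 2, so a 175-day look-back from visit 10 could perhaps be filled for everyone. That reading would count days before treatment: 175 - 168 = 7 for a visit at week 24, and 175 - 161 = 14 at week 23. It is not a sensible post-treatment outcome, and it still depends on visit date. A third reading, requiring a complete record to day 175, would exclude participants seen on schedule under the complete-case rule. None of these readings fits the stated denominator.

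2. **The SAP declares the derivation unfinished.** It does, so the matter can be settled before analysis. As it stands, 175 is the only denominator in either document.

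3. **The effect is small.** On the scale of the comparison this largely stands. The documents give no standard deviation. Assuming 20 to 40 points and 48 participants per drug arm, the 95% half-width is 1.96 x SD x sqrt(2/48), about 8 to 16 points. The 0.4-point loss on a 10-point difference is then 2.5% to 5% of the half-width. If every visit fell at week 24, estimate and interval would shrink by the same factor. Randomisation and blinding to drug make a timing difference between arms less likely, though they do not rule one out. The understated arm means and the scores that move with visit date remain.

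4. **Dropping uncovered days is itself a missing-data choice.** It is: it treats uncovered days as resembling covered ones. That is milder than scoring them all as drinking days, but the plan should say so.

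**Conclusion.** The concern holds. The fixed 175 does not match the visit window or the scheduled last visit. With abstinent days counted from visit 2 to visit 10, a participant seen exactly on schedule cannot score above 96.0%, and full abstinence ranges over 8 points by visit date. The expected loss is about 4% of arm means and of true differences, given visits centred on week 24 and timing unrelated to arm or drinking. Any bias beyond that is possible but cannot be sized. Because the comparisons are labelled exploratory, no test decision is at risk. What is affected is the scale of a primary estimate, and it should be corrected before analysis.

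**What to change.** In Protocol 13.3.2 and SAP 5.3, replace the fixed 175 with each participant's own number of days covered by timeline follow-back from visit 2 to visit 10: 100 x days with no alcohol / days covered. State whether the day of visit 2 and the day of visit 10 are counted. As a ratio, the rule also handles gaps in the record and visits outside the window; the SAP should say that uncovered days leave both numerator and denominator.

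Optionally, add a sensitivity analysis of this outcome on the common window of days 1 to 161, with 161 as the denominator. The relapse outcome and the 3-month outcomes stay as they are.

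The cost is one clause in each document and no new data. Percentages will rest on slightly different lengths of follow-up: 161 to 175 days for in-window visits with complete records, and outside that range otherwise. The optional sensitivity analysis leaves out up to 14 observed days for some participants.

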### **13.3.3 Secondary outcome analysis**

There are 15 secondary outcomes (section 13.1.2); all of these outcomes will be reported descriptively on an ITT complete case basis; additionally, the between-group mean differences and 95% confidence intervals will be reported on an exploratory basis for the primary comparison (all ketamine participants versus all non-ketamine participants). Also, as a feasibility outcome, attrition will be reported as a proportion (with 95% confidence interval) overall and by arm.

### **13.3.4 Sensitivity and other planned analyses**

All participants will be in a state of detoxification at recruitment, hence in the event of loss to follow-up, it is not appropriate to make an assumption that the participant had or had not relapsed at 6 months. To address the issue of missing data due to loss to follow-up, a sensitivity analysis will be performed using multiple imputation methods, for relapse at 6-month follow-up only, making the assumption that all missing data were missing at random.

## **13.4 Randomisation methods**

See Section 7.2 for a full description of randomisation methods, block design will be used.

### **13.5 Interim analysis**

As an interim analysis with regards to trial continuation, attrition among participants receiving ketamine only will be determined; the trial will be discontinued if more than 21/24 (88%) of participants who were randomised to ketamine are lost to follow-up at 3 months. Only aggregate data will be provided to the statistician at 3-month follow-up to ensure that treatment arm allocation will remain concealed. Due to the short duration of follow-up, no interim analyses for the primary or secondary outcomes are planned. From a safety perspective, adverse events will be monitored by the trial team and any concerns will be addressed.

### **13.6 Other statistical considerations**

A full statistical analysis plan (SAP) will be presented to the TMG prior to commencing the analyses. Any amendments to the SAP will be recorded, with the nature of the amendment, the date of amendment and date approved by the TMG.

## **14 Name of Committees involved in trial**

A trial management group (TMG) will be put in place for this trial which consists of the Project Manager, CI, Lead Researcher, Co-Investigators, Trial Anaesthetist, Trial Statistician, Research Associate and Research Assistant. The terms of reference and current members of this committee will be held in the Trial Master File and can be provided upon request.

## **15 Direct Access to Source Data/Documents**

The investigator(s)/ institution(s) will permit trial-related monitoring, audits, REC review, and regulatory inspection(s), providing direct access to source data/documents. Trial participants are informed of this during the informed consent discussion. Participants will consent to provide access to their medical notes.

## **16 Ethics and regulatory requirements**

The sponsor will ensure that the trial protocol, patient information sheet, consent form, GP letter and submitted supporting documents have been approved by the appropriate regulatory body (MHRA in UK) and a main research ethics committee, prior to any patient recruitment.

Any changes in research activity and documentation, except those necessary to remove an apparent, immediate hazard to the participant in the case of an urgent safety measure, must in the first instance be reviewed by the Chief Investigator. All amendments, will be submitted by the CI to the sponsor who will assess if the amendment is substantial or non-substantial. Substantial amendments to the protocol and other trial

related essential documents as assessed by the sponsor will be submitted in writing to the appropriate REC, Regulatory Authority and Trust Research & Development (R&D) for approval prior to implementation of amended documents.

Before the site can enrol patients into the trial, the Chief Investigator/Principal Investigator or designee must apply for NHS permission from their Trust Research & Development (R&D) and be granted written permission. It is the responsibility of the Chief Investigator/Principal Investigator or designee at each site to ensure that all subsequent amendments gain the necessary approval. This does not affect the individual clinician's responsibility to take immediate action if thought necessary to protect the health and interest of individual patients (see section 10.5.6 for reporting urgent safety measures).

Within 90 days after the end of the trial, the CI/Sponsor will ensure that the main REC and the MHRA are notified that the trial has finished. If the trial is terminated prematurely, those reports will be made within 15 days after the end of the trial. The CI will supply the Sponsor with a summary report of the clinical trial, which will then be submitted to the MHRA and main REC within 1 year after the end of the trial.

## **17 Monitoring requirement for the trial**

A trial specific monitoring plan will be established for studies. The trial will be monitored with the agreed plan.

## **18 Finance**

This trial is being funded by the Medical Research Council.

## **19 Insurance**

University College London holds insurance against claims from participants for injury caused by their participation in the clinical trial. Participants may be able to claim compensation if they can prove that UCL has been negligent. However, as this clinical trial is being carried out in a hospital, the hospital continues to have a duty of care to the participant of the clinical trial. University College London does not accept liability for any breach in the hospital's duty of care, or any negligence on the part of hospital employees. This applies whether the hospital is an NHS Trust or otherwise.

Participants may also be able to claim compensation for injury caused by participation in this clinical trial without the need to prove negligence on the part of University College London or another party. Participants who sustain injury and wish to make a claim for compensation should do so in writing in the first instance to the Chief Investigator, who will pass the claim to the Sponsor's Insurers, via the Sponsor's office.

Hospitals selected to participate in this clinical trial shall provide clinical negligence insurance cover for harm caused by their employees and a copy of the relevant insurance policy or summary shall be provided to University College London, upon request.

## 20 Publication policy

All proposed publications will be discussed with Sponsor prior to publishing other than those presented at scientific forums/meetings. Please refer to UCL publication policy.

## 21 Statement of compliance

The trial will be conducted in compliance with the approved protocol, the UK Regulations, EU GCP and the applicable regulatory requirement(s).

